6. *Self-Regulation Mechanisms Hypotheses:* In 4 different fMRI tasks, we hypothesize (a) greater activation of anterior cingulate cortex (ACC) and medial orbitofrontal cortex (OFC) and decreased activation in amygdala/hippocampus after MTPC intervention compared to before intervention (i.e. a pre-post increase) in an emotional Go/NoGo inhibitory control task; (b) greater activation of insula after (compared to before) MTPC in a self-compassion task (that contrasts self-reassurance conditions with a self-criticism condition); (c) greater insula activation during an interoceptive attention task (that contrasts an interoceptive attention condition with an exteroceptive attention condition); and (d) greater rostral ACC (rACC) and ventromedial prefrontal cortex (vmPFC) activation during the anticipation of pain and greater activation in the lateral prefrontal cortex (LPFC) and somatosensory areas during pain in an emotion/pain regulation task, after compared to before the MTPC intervention.
We hypothesize that all inhibitory control and interoceptive targets will be associated with higher levels of initiation of regimen adherence, while self-compassion, interoceptive targets and emotion/pain regulation will be associated with higher levels of regimen maintenance.

HEART Pilot Study Hypotheses

7. ***HEART pilot study validation goal:*** Our goal is to implement activity and heart-rate tracking, nutrition, sleep, and mindfulness practice tracking in a cohort of MINDFUL-PC alumni to determine whether this suite of behavioral monitoring tasks can behaviorally validate the signal from the self-reported action plan initiation protocol.

We hypothesize that self-reported action plan initiation with activity, diet, sleep or mindfulness practice will be associated with a behavioral change as assessed with the daily tracking devices.

8. ***HEART pilot study concurrent cohort:*** We hypothesize that participants who are in an 8-week MTPC group will demonstrate higher levels of action plan initiation, with an associated change in behavioral monitoring, than participants who are randomized to the waitlist condition. We also hypothesize that participants who chose to increase activity will have a greater increase in daily activity than those who chose a diet-, mindfulness- or sleep-related action plan goal.

B. Background and Rationale:

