All patient participants will receive an ongoing 3-5 minute Participant Engagement phone call from a member of the study staff. This call will be made according to the brief phone script attached. This call will be made every two weeks during Study Weeks 1-8. The purpose of this outreach call will be to provide support for patients in both groups, help participants cultivate a relationship with study staff, give participants a place to ask questions, and support participants in completing study visits. The call will have five talking points: 1) How have you been in the last 2 weeks? 2) Have you had any issues with completing the weekly Mindfulness Practice Diary or the Mindfulness Resources Use Diary? 3) Have there been any issues with your participation in the study in general? 4) We appreciate your contribution to the research study and encourage you to continue filling out the diaries – just as a reminder you will receive \$20 for each survey session and \$20 if you complete all the weekly diaries. 5) Is there anything else you'd like to share with us? Study staff will complete a call log for all engagement calls, and issues raised in these calls will be discussed twice a week in research staff meetings.

Mindfulness Intervention (MTPC Intervention Group; PT Study Week 1-8):

Patients in the 8-week MTPC program will meet with a behavioral care provider for 8 weeks in groups of approximately 6-12 participants, to receive 2 hours of instruction in MTPC. MTPC groups will be generally held in the evenings in clinical spaces within each participating CHA primary care health center. Between weeks 6 and 7 there will be a weekend 7 hour long day of silent practice at locations within the local community or within a nearby CHA hospital facility space. The total duration of the program is 23 hours over 8 weeks with additional expectations

for daily home practice by participants. Details about this intervention can be found in section C.3.e.4.

Action Plan Study Session (Completed between PT Study Weeks 6-7):

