During Patient Study Weeks 6-7, all patients participating in the MINDFUL-PC program will fill out an Action Plan Worksheet and watch a brief SMART goal video (for example: <https://www.youtube.com/watch?v=1-SvuFIQjK8>), which is designed to support the creation of a short-term health goal. Patients randomized to the 8-week MTPC group will receive instruction and support during the group in developing health goals for a short-term action plan, and communicating these goals effectively to people in their life who might be important stakeholders in their health. Duration: 15 minutes.

After completing the Action Plan Worksheet, patient participants will complete the Action Plan Assessment (APA-10), a 10-item scale that evaluates patient behavior in the domains of self-determination, motivation, shared decision-making, and barrier appraisal. This survey will be completed online in REDCap or on paper, and is expected to take the average patient 5 minutes to complete.

Post-treatment Survey Session Computer Visit 1 (Completed between PT Study Weeks 8-12):

After eight weeks, participants in both groups will be asked to complete another series of surveys online on REDCap or on paper. Patient participants will again be given the option to either complete the surveys on a device at their PCMH or outside of the office on a computer of their choosing. Electronic devices will be provided to patients in the 8-week MTPC group so that they may complete their surveys at their PCMH in the hour following their final weekly meeting. Paper survey answers will be transferred to a secure REDCap database by MINDFUL-PC study staff, and all paper surveys will be stored in a double-locked filing cabinet. Research assistants (to be hired later) will be available at several scheduled 1-hour sessions at PCMH sites to bring electronic devices and offer support for survey completion. Patients assigned to the 6-month waiting list may visit their PCMH to use a device to complete their surveys during one of these scheduled sessions.

In this session, patient participants will complete the Patient Mindfulness Self-Report Battery, the Patient Clinical Assessment Battery, the Patient Self-Management Battery, the Patient-PCP Relationship Battery, the Action Plan Initiation Survey (APIS-5), the Weekly Mindfulness Practice Diary, the Patient Satisfaction Survey, and the Adverse Event Reporting Form. These surveys are expected to take the average patient 65 minutes to complete.

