This hour-long informational session will involve both experiential and informational introduction sections. The class will begin by answering the question “What is mindfulness?” and group leaders will offer evidence for supporting mindfulness. Group leaders will then guide the class in an experiential session. The orientation session is designed to foster a commitment to do the 30 minutes or more per day at home practice; to give the participants a ‘taste’ of the mindfulness practices that will be presented in the classes and to process with the prospective participant the experience of the practice; to inform the patient about the logistics of the class; to review the specific upcoming course schedule; to meet the specific leaders for the upcoming group; to learn about risks and benefits of the MTPC program; and to give patients an

opportunity to ask questions. The orientation session will conclude with an explanation of internal and external resources for continuing mindfulness education, and will offer patients a referral to these resources.

C.3.e.4 MTPC:

Mindfulness Training for Primary Care (MTPC), is a modified version of MBSR for delivery as group psychotherapy modality within patient-centered medical homes. MTPC offers a series of eight weekly, two-hour core sessions delivered in a group format with a seven hour day of silent practice between weeks 6 and 7. MTPC will follow the same structure as MBSR, but will also include a weekly topic to be discussed for 20 minutes per class for each of the 8 weeks and the integration of a PCP illness management/health maintenance appointment to be held during week 6-7 of the group. The weekly themes are as follows:

Part A: Sessions 1-4 are primarily focused on learning to pay attention.

Week 1: From Autopilot to Befriending the Body and Mind

Week 2: Perception and Rediscovering “Beginner’s Mind”

Week 3: Pleasure and Freedom in Being Present

Week 4: Staying Present with Pain, Difficulty, Illness and Stress

Part B: Sessions 5-8 are focused on illness self-management and skills for changing health behaviors.

Week 5: Allowing What Is: The Bedrock Needed to Support Change

Week 6: Skillful Action and Skillful Communication

Week 6-7 Action Plan Worksheet: The purpose of this worksheet is to support the patient in generating his/her own short-term action plan.

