The **Perceived Control Questionnaire (PCQ)** is adapted from a 5-item perceived control measure from Jerant et al. [55] and a previously validated survey from Armitage et al. [56]. This 5-item scale ask participants to rate their sense of control over chronic illness self-management on a 7-point scale from 1 (*None*) to 7 (*Total*). Items include "How much personal control do you have over your self-management behaviors?" Duration: 3 min.

Action Plan Worksheet/SMART Goal Video: Patient participants will complete the Action Plan Worksheet and watch a brief video about creating SMART goals (for example, <https://www.youtube.com/watch?v=1-SvuFIQjK8>) in PT Study Week 7. The Action Plan Worksheet is a 13-item worksheet that incorporates information about SMART goals to support patient participants to make a goal about their health in one of 3 categories (activity level/exercise, diet/eating/drinking, or mindfulness meditation practice). Patients are encouraged to share this worksheet with a person who may help the patient in accomplishing the goal, and/or a healthcare provider. Duration: 15 min.

Patients will complete the self-report **Action Plan Assessment (APA-10)** questionnaire after filling out the Action Plan Worksheet, at PT Study Week 7. This survey instrument is developed as an adaptation of two self-determination theory scales [57] [58] and incorporates elements of shared decision-making [59] and self-efficacy and barrier appraisal [60]. This 10-item scale evaluates patient behavior in the domains of self-determination, motivation, shared decision-making, and barrier appraisal. Participants are asked to rate their agreement with a statement on

a 7-point scale from 1 (*Strongly Disagree*) to 7 (*Strongly Agree*). A sample item includes “I have agreed to this action plan because I want to do it for myself.” Duration: 5 minutes.

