Patient participants in the MTPC Group and in the Waitlist Group will complete the mindfulness practice diary card every week for patient study weeks 1-8, throughout their MTPC training. Both groups of patient participants will complete this card for the week preceding the post-treatment survey session and the week preceding the follow-up survey session. Participants in the **concurrent cohort** of the HEART pilot study will also complete this survey for 1 week prior to MTPC Session 1 and for four weeks during MINDFUL-PC study weeks 5 and 9.

C.3.f.10. Mindfulness Resources Use Survey:

The **Mindfulness Resources Use Survey** is a 7-item weekly survey that asks about the frequency of use of community or mobile mindfulness resources as listed on the Community Resources handout given to all patients during the orientation session. This survey asks patients whether they have visited local mindfulness or meditation centers in person, whether they have used mindfulness guided recordings or apps online, and whether they have read any mindfulness-related books. It also asked about some related activities where people often practice mindfulness such as yoga, spiritual activities, and places of worship. A patient's total mindfulness resource utilization will be calculated by study personnel weekly. This survey will be completed by every study participant for Study weeks 1-8, and during the Follow-Up Survey Session at patient study week 36. Participants in the MTPC group will fill out the resources diary on a scantron sheet, and participants in the control group will fill out the resources diary on an online REDCap form. Participants in the **concurrent cohort** of the HEART pilot study will also complete this survey for 1 week prior to MTPC Session 1 and for four weeks during MINDFUL-PC study weeks 5 through 9. Duration: 5 min.

C.3.f.11. Reports from Electronic Medical Records for Patient Participants:

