Mixed Effects Modeling to evaluate for main effects of PCP mindfulness training and main effects of Patient training level (1 hour vs. 8 week) for each survey, as well as the interaction effect with relevant covariates.

3. *Health Outcomes Hypotheses*: We hypothesize reductions in depression, anxiety and stress as a main effect of MTPC. Finally, we hypothesize reductions in use of medications prescribed for symptom reduction (benzodiazepines, opioids, etc.), overall improvement in markers of health maintenance and chronic illness management (i.e. PQRS data). We hypothesize the highest levels of initiation and maintenance of self-management action plans among MTPC group with Mindfulness-trained providers.

Mixed Effects Modeling to evaluate for main effects of PCP mindfulness training, main effects of Patient training level (1 hour vs. 8 week) for each outcome, as well as the interaction effect with relevant covariates.

4. *Provider Resilience Hypothesis*: We hypothesize greater workplace well-being, reduced experience of burnout, and increased resiliency among providers as a main effect of provider MBSR + Mindful Communication training.

We will use Mixed Effects Modeling to evaluate for main effects of PCP mindfulness training and time for each survey and the interaction of the two.

5. *Medical Regimen Adherence Hypotheses*: We hypothesize a main effect of MTPC group status on levels of initiation and maintenance of medical regimen health behavior change, as measured by the APIS-5 self-report score. The highest levels will be demonstrated among the MTPC group participants with mindfulness-trained providers. We hypothesize that total formal mindfulness practice, post-study total mindfulness score, baseline mindful non-judgment score, and self-compassion will be associated with successful initiation and maintenance of action plans. Action plan initiation will be validated by increases in step count, and increases in number of active periods, changes in sleep, changes in mindfulness practice, and changes in nutritional habits.

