Using an intent-to-treat analysis, we will use logistic regression and Mixed Effects Modeling to evaluate for main effects of MTPC, mindfulness-trained PCPS, and the interaction of the two on binary and continuous ratings of level of action plan initiation and maintenance. We will conduct exploratory linear regression models of post-study mindfulness and self-compassion and overall practice dose as independent variables with level of action plan initiation and maintenance as dependent variables.

The experimental fMRI pilot analyses methods are described below.

6. *Self-Regulation Mechanisms Hypotheses*: In 4 different fMRI tasks, we hypothesize (a) greater activation of ACC and OFC and decreased activation in the amygdala/hippocampus after MTPC intervention compared to before intervention (i.e. a pre/post increase) in an emotional Go/NoGo inhibitory control task, as in Perez 2016 [69], using validated emotional pictures (International Affective Pictures System, IAPS, [70]). The task includes 448 IAPS pictures (50% neutral and 50% unpleasant), which will

be presented briefly (1.5 seconds), while participants either react (Go) or withhold a button press reaction (NoGo), depending on abstract symbols presented on top of the pictures; (b) greater activation of mid-posterior insula after (compared to before) MTPC in a self-compassion task (that contrasts a self-reassurance condition with a self-criticism condition), as in Longe 2010 [71]; (c) greater insula activation during an interoceptive attention task (that contrasts an interoceptive attention condition with an exteroceptive attention condition) as in Farb 2013[72], and d) increases in the rostral ACC (rACC) and ventromedial prefrontal cortex (vmPFC) during the **anticipation of pain** after compared to before MTPC and increased activation in the lateral prefrontal cortex (LPFC) and somatosensory areas **during pain** after compared to before the MTPC, as in Kim 2013 [73]. We hypothesize that all inhibitory control and interoceptive targets will be associated with higher levels of initiation of regimen adherence, while self-compassion, emotion/pain regulation, and interoceptive targets will be associated with higher levels of regimen maintenance.

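### Does pooling all action plan goals, mindfulness practice included, undermine the medical regimen adherence comparison?

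*Combined protocol and SAP*

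**What the plan says.** C.3.f.6 describes a worksheet, completed around weeks 6-7, that is intended to "support patient participants to make a goal about their health in one of 3 categories (activity level/exercise, diet/eating/drinking, or mindfulness meditation practice".

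C.5.b item 5 sets out its hypothesis in these words: "main effect of MTPC group status on levels of initiation and maintenance of medical regimen health behavior change, as measured by the APIS-5", which patients report themselves. The analysis is intention to treat. It uses logistic regression and mixed models to test MTPC, PCP training and "the interaction of the two on binary and continuous ratings of level of action plan initiation and maintenance". Exploratory regressions add mindfulness, self-compassion and practice dose as predictors. Goal category is not a model term, a subgroup or a table row.

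Five other places bear on this:

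- **C.3.d.2, Mindfulness Intervention.** The MTPC programme carries additional expectations "for daily home practice by participants".
- **C.3.d.2, Action Plan Study Session.** All patients fill in the worksheet, but only MTPC patients "will receive instruction and support during the group in developing health goals for a short-term action plan".
- **C.3.e.3.** The orientation, which both arms attend before randomisation, is "designed to foster a commitment to do the 30 minutes or more per day at home practice".
- **C.3.f.9.** Patients "in the MTPC Group and in the Waitlist Group will complete the mindfulness practice diary card every week" during weeks 1-8.
- **A.2.b item 7 (HEART pilot).** The hypothesis is that "self-reported action plan initiation with activity, diet, sleep or mindfulness practice will be associated with a behavioral change". C.5.b item 5 likewise names a change in mindfulness practice among the things that validate initiation.

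**The concern.** One of the three permitted goals is the behaviour that the intervention trains. A patient in MTPC who picks meditation practice as the action plan goal and goes on practising counts as an initiator for doing what the course already asked. The goal is set after randomisation and with group support in one arm only, so the mix of goals may well differ between arms.

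If practice goals are also easier to meet, the pooled initiation rate could be higher in MTPC with no gain on activity or diet goals. The hypothesis is worded as an effect on medical regimen behaviour, and a reader could take a positive result to mean more than it does. The planned output would not separate the cases. The goal-specific analyses in the HEART pilot do not fill the gap: they are not by arm, and D.4.c calls that pilot underpowered for between-group comparison. The sample size section adds to the worry, because the 0.68 assumed for MTPC comes from rates of meditation practice in earlier programmes.

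**Working it through.** **Inputs from C.5.c.** 290 MTPC and 144 control patients; initiation 0.68 and 0.54; two-sided 0.05; stated power 80%.

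**The plan's own figure.** Pooled rate = (144 × 0.54 + 290 × 0.68)/434 = 0.634. Standard error under the null = √[0.634 × 0.366 × (1/144 + 1/290)] = 0.0491. Standard error under the alternative = √[0.54 × 0.46/144 + 0.68 × 0.32/290] = 0.0498. Power = Φ[(0.14 − 1.96 × 0.0491)/0.0498] = Φ(0.88) = 81%. Exact binomial enumeration also gives 81%. The stated 80% reproduces.

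**Model for goal mix alone.** Let q be the share of an arm choosing practice and s the success rate on practice goals. Other goals succeed at 0.54 in both arms, so MTPC has no effect within any category.

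- Arm rate = 0.54(1 − q) + s·q
- Shift in the arm difference = (s − 0.54)(q in MTPC − q in control)

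The documents give no value of q, so every share below is an assumption. For s they give one practice-based rate, 0.68.

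**Results at s = 0.68.** MTPC rates are 0.568, 0.582 and 0.595 for q = 20%, 30% and 39%. Each cell shows the shift in percentage points, then the exact chance of a significant result favouring MTPC.

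| Controls choosing practice | MTPC 20% | MTPC 30% | MTPC 39% |
|---|---|---|---|
| 0% | 2.8; 8% | 4.2; 13% | 5.5; 19% |
| 10% | 1.4; 5% | 2.8; 8% | 4.1; 13% |
| 20% | 0.0; 3% | 1.4; 5% | 2.7; 8% |
| 30% | −1.4; 1% | 0.0; 3% | 1.3; 5% |

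With no difference between arms, this one-direction chance is about 2.5%, so entries of 3% and 5% are at or near the floor. The 0% row is unlikely, since both arms attend the same orientation and keep practice diaries.

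**Higher success rates, purely hypothetical.** At s = 0.90 the chances are 11%, 31% and 57% with 10% of controls choosing practice, and 2.5%, 11% and 30% with 20%. The 39% share is not neutral here: (0.90 − 0.54) × 0.39 = 14.0 points, which is the whole planned effect.

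**Wider shares, also hypothetical.** Suppose 20% of controls and 70% of MTPC patients choose practice, s = 0.68, and other goals succeed at 0.505 so that the control rate stays at 0.54. The MTPC rate is 0.70 × 0.68 + 0.30 × 0.505 = 0.627, a shift of about 9 points, significant about 42% of the time.

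**What a category table could show.** Suppose MTPC works equally on every goal (0.68 vs 0.54), with practice chosen by 39% vs 10%.

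- Other goals met, over all randomised: 0.61 × 0.68 = 0.415 vs 0.90 × 0.54 = 0.486. This looks like harm.
- Practice goals met, over all randomised: 0.39 × 0.68 = 0.265 vs 0.10 × 0.54 = 0.054. This looks like an effect on practice alone.
- Within category, the rates are 0.68 vs 0.54 throughout. But only about 14 controls hold practice goals (0.10 × 144), so the 95% interval on that difference is about ±27 points.

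**The case for a change.** The strongest case for a change is about interpretation. The hypothesis speaks of medical regimen behaviour, and a result driven by meditation goals supports a narrower statement than one driven by activity or diet. The practice diaries and dose models show how much patients practised, not which goal they chose or met. A descriptive table would cost little, and fixing its form in advance would avoid choosing a presentation after seeing the data. It is also true that no such table is planned, and that the effect of goal mix would be large if practice goals were far more common in MTPC and met far more often than 0.68.

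The part that stands is that the pooled result alone cannot be attributed to one kind of goal. Three things limit it.

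First, leading patients to choose and meet practice goals is part of what MTPC does after randomisation. It is not confounding of the any-goal comparison.

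Second, other planned data bear on which behaviours changed. Practice diaries and the TFEQ-R18 eating questionnaire are collected in both arms at post-treatment and follow-up (Appendix A, Table 3), and C.3.f.11 draws BMI and meat-eating frequency from the record. The main trial has no comparable activity measure, so this cover is partial.

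Third, the table would not settle the question. Goal choice follows randomisation, and each denominator can mislead, as the last calculation shows.

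A related mismatch is clerical. The APIS-5 description in C.3.f.6 lists six goal categories with none for mindfulness, refers to goals made with the PCP, and gives weeks 8, 12 and 16. C.3.d.2 has patient-completed worksheets and separate APIS-5 sessions at weeks 9, 10 and 16. The version 1.5 log records that the APIS-5 was modified to match the worksheet, so the description looks like carried-over text. The worksheet category identifies practice goals without it.

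**Conclusion.** The observation is accurate, but it does not call for a change. The comparison tests whether MTPC raises initiation and maintenance of any self-chosen goal, practice included. That is a legitimate question, protected by randomisation and consistent with how the documents define initiation. The missing breakdown is a reporting choice. The worksheet records the category, so analysts can tabulate goals by arm when they write up, and the table would alter neither the test, the sample size nor the conclusion.

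At the one documented practice rate (0.68), with assumed shares of 20% to 39% in MTPC and 10% to 20% in control, goal mix alone moves the difference by 0 to 4.1 points against the planned 14. The chance of a significant result favouring MTPC is then 3% to 13%, against a floor of about 2.5%. With no controls choosing practice, the most the shift reaches over those MTPC shares is 5.5 points. The larger figures need a practice success rate well above 0.68 or a much wider gap in goal choice, and the documents support neither. All the shares are assumptions, so the true size is unknown. The reading of the pooled test as an any-goal comparison does not depend on them.
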